### 7.7.1 Analysis of Primary Efficacy Endpoint

The primary study analysis will be to evaluate the proportions of primary composite responders (defined in Section 7.1) over 12 weeks of treatment between the eluxadoline and placebo groups. These 2 proportions are represented as  $\pi_{\text{eluxadoline}}$  and  $\pi_{\text{Placebo}}$ . The primary hypotheses for this study are described below:

$$H_0: \pi_{\text{eluxadoline}} - \pi_{\text{Placebo}} = 0$$

Vs

$$H_A: \pi_{\text{eluxadoline}} - \pi_{\text{Placebo}} \neq 0$$

The numbers of responder and non-responder patients and corresponding percentages will be summarized and presented in a summary table by treatment group. Treatment effect will be assessed using the chi-square test.

As supportive analysis, the primary endpoint will be analyzed using logistic regression model that will include treatment group as a factor and baseline pain score and stool consistency score as covariates.

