### **3.1.1 Rationale of Study Design**

In the Phase 3 studies that established the efficacy and safety of eluxadoline in the treatment of IBS-D, patients were prospectively asked about loperamide use in the prior 12 months for IBS-D and whether treatment with loperamide had adequately controlled their symptoms; 36% (N=872) of patients reported using loperamide in the prior 12 months for their IBS-D symptoms. Of these, approximately 65% reported that use of loperamide failed to provide adequate control of their IBS-D symptoms (N=538). Similar to the results in the overall intent-to-treat (ITT) population, in patients who reported that loperamide did not provide adequate relief of IBS-D symptoms, the proportion of composite responders was significantly greater in the eluxadoline treatment groups as compared with placebo ( $p < 0.05$ ) for both eluxadoline 75 mg and 100 mg after 12 weeks of treatment. This prospective study is being conducted to further study the efficacy and safety of eluxadoline 100 mg BID in patients who self-report that loperamide failed to adequately control their IBS-D symptoms in the prior 12 months.

To be included in the trial, patients must have an average daily stool consistency score (BSS) of  $\geq 5.5$  and at least 5 days with a BSS score  $\geq 5$  on a 1-7 scale over the week prior to randomization and an average WAP score in the past 24 hours of  $> 3.0$  on a 0 to 10 scale over the week prior to randomization. Patients must report that use of loperamide in the 12 months to treat IBS symptoms prior to screening had failed to provide adequate control of their IBS-D symptoms. Additionally patients must have completed the ePRO diary on at least 5 of the 7 days during the week prior to randomization AND at least 10 of 14 days during the 2 weeks prior to randomization. The patient population under study is considered as appropriate for achieving the study objectives.

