## 7.5 Sample Size Calculations

Assuming a placebo response for the primary efficacy endpoint, composite response in pain and stool consistency rate at 12 weeks, of 13% and an approximate 14% treatment effect of eluxadoline over placebo, a sample size of 340 patients is required (1:1 randomization ratio, eluxadoline: placebo, 170 patients per arm). (From the Integrated Summary of Efficacy Report, patients refractory to loperamide in the pooled studies IBS 3001 and 3002 had 13% and 27% composite response in pain and stool consistency rates in the placebo and eluxadoline groups, respectively. This set of response rates are the same when using 40%

WAP improvement to replace the 30% in the primary efficacy composite responder criteria.) This sample size will have approximately 90% power to detect the difference of the primary efficacy endpoint response proportion between eluxadoline and placebo using a 2-sided chi-square test at a significance level of 0.05.

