## **10.2 Management of Protocol Amendments and Deviations**

### **10.2.1 Modification of the Protocol**

Any changes in this research activity, except those necessary to remove an apparent, immediate hazard to the patient, must be reviewed and approved by the sponsor or its designee. Amendments to the protocol must be submitted in writing to the principal investigator's or subinvestigator's IRB/IEC for approval before patients are enrolled into an amended protocol.

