2.2 Baseline Definition and Visit Window for Analysis

For the score of BSS, WAP, abdominal discomfort, and abdominal bloating, the baseline value is defined as the weekly average in the week prior to randomization.

For bowel movement, urgency episodes, and episodes of fecal incontinence, the baseline value is defined as the average number per day in the week prior to randomization.

For all other variables, the baseline value is the last observation prior to receiving the first dose of study medication as usual.

For weekly assessment such as treatment satisfaction and degree of relief of IBS symptoms, the visit window is defined as target day \pm 3 days. For example, the treatment satisfaction assessment is collected weekly, starting from end of Week 1, the visit window will be day 4 (- 3 days) -- day 7 (target day) -- day 10 (+ 3 days).

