2.3 Data Conventions

Based upon interactive voice response compliance data from the completed Phase 3 trials in patients with IBS-D, we are anticipating 15% to 20% missed ePRO diary entry days for those patients who were not discontinued. For this study, missed daily ePRO diary entries will not be considered as protocol violations. The minimum of the non-missing diary entries for each study endpoint will be specified in corresponding sections and the method of handling missing data for each endpoint is described in corresponding sections. Only observed data (i.e., no imputation) will be used for analyses except for the second definition of weekly composite responder (details are described in Section [6.5.1 14](#))).

If there is more than one visit within a visit window (e.g., unscheduled visits), the visit closest to the target date of the visit will be used for analyses. If two visits are equidistant from the target date, then the data from the later visit will be used for analyses.

If the date of a visit is out of the visit window, the data will only be displayed in listings.

All data collected will be displayed in listings.

3. Disposition and Exit Status

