6.3.1 Primary Analyses for Primary Efficacy Endpoint

The primary analysis is to evaluate the proportions of primary composite responders between the eluxadoline and placebo groups. These 2 proportions are represented as $\pi_{\text{Eluxadoline}}$ and π_{Placebo} . The primary hypotheses for this study are described below:

$$H_0: \pi_{\text{Eluxadoline}} - \pi_{\text{Placebo}} = 0$$

vs

$$H_A: \pi_{\text{Eluxadoline}} - \pi_{\text{Placebo}} \neq 0$$

The number and the percentage of responders and non-responders will be summarized in a table with p-value from chi-square test to test the different response rates between treatment groups.

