6.3.2 Other Analysis for Primary Efficacy Endpoint

As a supportive analysis, the primary endpoint will also be analyzed using logistic regression model with treatment group, the baseline pain score, and the baseline stool consistency score as exploratory variables.

[figure not shown]

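### The primary chi-square is valid and powered as stated, but it leaves the prespecified baseline pain and stool scores unused, and no interval for the difference in proportions is named in the visible text

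*Protocol*

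**What the plan says.** Protocol 7.7.1 states the null and alternative hypotheses on the difference between the two responder proportions, then says "Treatment effect will be assessed using the chi-square test". SAP 6.3.1 repeats the hypotheses and describes the output: "The number and the percentage of responders and non-responders will be summarized in a table with p-value from chi-square test". The protocol synopsis names the same test. Protocol 7.5 sizes the trial on the same difference, claiming "approximately 90% power to detect the difference of the primary efficacy endpoint response proportion between eluxadoline and placebo" with 170 patients per arm at 13% on placebo and 27% on eluxadoline.

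The two baseline scores appear only in support. SAP 6.3.2 plans a "logistic regression model with treatment group, the baseline pain score, and the baseline stool consistency score", as protocol 7.7.1 does. SAP 2.2 fixes how they are measured: for BSS and WAP, "the baseline value is defined as the weekly average in the week prior to randomization".

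No visible section names a confidence interval for the difference in proportions, an effect measure for the logistic model, or whether the chi-square carries a continuity correction. SAP 6.1 and 6.2 and parts of protocol 7.7 are not visible, so a general interval rule there cannot be excluded.

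**The concern.** Nothing here is invalid. Two things are left undone that could be settled at almost no cost.

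First, both scores are collected before randomization, defined in the SAP and already chosen as covariates, yet the primary analysis does not use them. If they predict response, the primary comparison is less precise than it could be with the same 340 patients. The supportive model does not fill the gap, because its treatment coefficient is a conditional log odds ratio and not the difference named in the hypotheses.

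Second, the interval method and the form of the chi-square are open in the visible text. The percentages show the point difference and an unadjusted interval follows from the counts, so no information is lost. But choices left until after unblinding can be made with the results in hand, and in a close trial the continuity correction alone can decide significance.

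**Working it through.** **1. The plan's own power.** Inputs from protocol 7.5 and 7.7: p0 = 0.13, p1 = 0.27, d = 0.14, 170 per arm, two-sided alpha 0.05. The mean rate is 0.20.

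n per arm = [1.960 × sqrt(2 × 0.20 × 0.80) + 1.282 × sqrt(0.13 × 0.87 + 0.27 × 0.73)]² / 0.14² = (1.109 + 0.714)² / 0.0196, which rounds up to 170, or 340 in total.

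Power at 170 per arm is 90.1% by the same formula. Exact binomial enumeration of the uncorrected test gives 90.7%. The plan's figure reproduces.

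**2. Continuity correction.** The corrected formula needs 184 per arm, so the planned N matches the uncorrected test. With the correction, exact power at 170 per arm is 87.9%. Exact type I error at 20% in both arms is 5.1% uncorrected and 3.6% corrected.

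An edge case shows the effect. With 22/170 against 36/170 responders, the difference is 14/170 = 8.2 points and the pooled rate is 58/340 = 0.1706, so the standard error is sqrt(0.1706 × 0.8294 × 2/170) = 0.0408.
- Uncorrected: z = 0.0824/0.0408 = 2.02, p = 0.044.
- Corrected: z = (0.0824 - 1/170)/0.0408 = 1.87, p = 0.061.

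**3. The interval.** For 22/170 against 46/170, close to the planned rates, the difference is 24/170 = 14.1 points, Newcombe 95% CI 5.6 to 22.4. For 22 against 36, the Newcombe CI is 0.2 to 16.2 and the Wald CI 0.3 to 16.2.

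**4. Gain from adjustment.** Fit the SAP 6.3.2 logistic model. For every ITT patient predict response under eluxadoline (m1) and under placebo (m0). The estimate is D = mean(m1 - m0). With t = 1 for eluxadoline and equal arms, patient i has influence value

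IF = 2t(y - m1) - 2(1 - t)(y - m0) + (m1 - m0) - D,

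and SE = sqrt(sum(IF²)/(N - 4)/N).

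The gain depends on how much outcome variance the scores explain, which the documents do not give, so a range is assumed. Each setting has 20,000 simulated trials, 170 per arm, with marginal rates fixed at 13% and 27%. WAP was drawn from a normal truncated to 3–10 and BSS from a normal truncated to 5.5–7: ranges from protocol 3.1.1, shapes assumed, scores equally weighted. The unadjusted half-width is 8.33 to 8.34 points. Patient equivalents are ((unadjusted/adjusted half-width)² - 1) × 340.

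| Variance explained (assumed) | Odds ratio per SD of combined score | Change in power (points) | Adjusted CI half-width (points) | Equivalent patients |
|---|---|---|---|---|
| 0% | 1.00 | -0.06 | 8.36 | -2 |
| 1.3% | 1.35 | +0.35 | 8.31 | +2 |
| 2.9% | 1.57 | +0.69 | 8.24 | +8 |
| 5.8% | 1.92 | +1.46 | 8.12 | +19 |
| 10.3% | 2.46 | +2.82 | 7.91 | +37 |
| 14.4% | 3.00 | +3.66 | 7.74 | +54 |

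The Monte Carlo standard error of the power change is 0.07 to 0.16 points. As a cross-check, replace n by n/(1 - R²): at R² = 0.05, 170/0.95 = 178.9 per arm gives power 91.5%, and the half-width is 8.37 × sqrt(0.95) = 8.16 points. This agrees with the 5.8% row.

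**5. Does adjustment cost validity?** Coverage was 94.7% to 95.2%. Type I error at 13%/13% and 20%/20% was 4.9% to 5.3% adjusted and 4.8% to 5.4% for the chi-square. One smaller run (4,000 trials, normal covariates, R² about 0.08, same N - 4 divisor) gave 6.0% against 5.3% for the chi-square, with Monte Carlo error of about 0.3 to 0.4 points. Runs of 15,000 trials with normal covariates gave 5.1% to 5.5% adjusted against 5.0% to 5.4%, so the 6.0% did not recur.

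Two misspecified cases (10,000 trials each):
- Curved covariate effect: power 93.1% adjusted against 90.6%, coverage 94.8%.
- Effect in one arm only: power 91.2% against 91.0%, coverage 95.1%.

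Type I error in both was 5.5% adjusted against 5.4% (standard error 0.23 points). No fit failed to converge in 400,000.

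**The case against.** The case for leaving the plan alone is a serious one. The chi-square is valid, the documents agree on it, no visible stratification factor is omitted, and it is the test that sized the trial. The covariate-adjusted model is already prespecified as support, and under that model a zero treatment coefficient implies a zero difference in proportions. The expected gain is small: eligibility restricts both scores, and pain response is already measured relative to baseline, so the top two rows of the table have no visible support. Newcombe and Wald intervals hardly differ. The continuity-correction example was chosen where the two versions disagree; at 22 against 46 responders both are clear (p = 0.001 and 0.002). A lighter remedy would name the uncorrected test, add an unadjusted difference with its interval, standardize the supportive model, and leave the primary test as it is.

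Most of this stands, and it sets the priority of the point. It does not remove the point. The correction is still unstated, the interval and adjusted estimate are not fixed in the visible text, and adjustment costs almost nothing if the scores are uninformative (half-width 8.36 against 8.34 points). The lighter remedy secures the reporting gain but leaves the primary comparison without the precision gain.

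**Conclusion.** The point holds as a worthwhile improvement, not as an error. The stated power of about 90% is correct for the uncorrected chi-square. Standardizing the planned logistic model would put the primary result on the scale of the hypotheses and add precision if the baseline scores predict response.

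The likely size is small: under 1 point of power, and at most about 8 patients' worth of precision, if the scores explain no more than 2.9% of outcome variance. Larger gains need prognostic strength that the documents do not show. The figures rest on the planned 13% and 27%, the assumed covariate shapes and the assumed range of variance explained. Confidence is moderate, because that prognostic strength is unknown and an interval rule may exist in text that is not visible.

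**What to change.** Revise SAP 6.3.1 before unblinding, as follows.

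- **Primary analysis:** the difference in responder proportions, standardized over the ITT population from the SAP 6.3.2 logistic model (treatment, baseline WAP, baseline BSS), with an influence-function standard error using the N - 4 divisor, a 95% CI and a two-sided p-value. If the arms are unequal, replace the factor 2 in the influence value by N divided by that arm's size.
- **Supportive analysis and fallback:** the chi-square without continuity correction, with the unadjusted difference and its Newcombe 95% CI. This becomes primary only if the model does not converge.
- **Missing baseline average:** fill with the pooled mean. This should be rare, since "patients must have completed the ePRO diary on at least 5 of the 7 days during the week prior to randomization". SAP 2.3 needs a stated exception, because it now says "Only observed data (i.e., no imputation) will be used for analyses except for the second definition of weekly composite responder".
- **Records:** enter the change in SAP section 9, align the test named in the protocol synopsis and in protocol 7.5 and 7.7.1, and note that the chi-square sample size remains approximately valid or slightly conservative.

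This adds no patients and no data. It does change the named primary test, so it must be fixed before the unblinding that follows database lock (protocol 5.1). The SAP Introduction gives the SAP precedence where the documents differ, but the sponsor must still decide whether the protocol needs amending. If so, protocol 10.2.1 applies: "Amendments to the protocol must be submitted in writing" to the IRB/IEC.

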### 7.7.2 Analysis of Secondary Efficacy Endpoint

The proportions of stool consistency responders and pain responders (defined in Section 7.2) over the 12-week treatment period and at each 4-week interval (weeks 1 to 4, 5 to 8, and 9 to 12) will be analyzed similar to the primary endpoint analysis.

The proportion of monthly composite responders (defined in Section 7.2) at each 4-week interval (weeks 1 to 4, 5 to 8, and 9 to 12) will be analysed similar to the primary endpoint analyses.

[REDACTED]

[REDACTED]

[REDACTED]

[REDACTED]

[REDACTED]

[REDACTED]

[REDACTED]

[REDACTED]

[REDACTED]

[REDACTED]

[REDACTED]

[REDACTED]

### **7.7.6 Other Analyses**

Not applicable.

### **7.7.7 Interim Analyses**

There will be no interim analysis for this study.

## **7.8 Handling of Missing Data**

Based upon interactive voice response compliance data from the completed Phase 3 trials in patients with IBS-D, we are anticipating on the order of 15% to 20% missed ePRO diary entry days for those patients who have not discontinued. For this study, missed daily ePRO diary entries will not be considered as protocol violations. Adequacy of non-missing diary entries for each study endpoint has been defined specifically in the primary, secondary, and additional endpoints sections of this protocol; patients will be considered as non-responders for the corresponding endpoints if the adequacy criteria are not met.

Detailed missing data strategies will be defined in the study SAP.

## **7.9 Data Quality Assurance**

To ensure compliance with Good Clinical Practice (GCP) and all applicable regulatory requirements, Allergan may conduct a quality assurance audit of the site records and regulatory agencies may conduct a regulatory inspection at any time during or after the study. In the event of an audit or inspection, the investigator (and institution) must agree to grant the auditor(s) and inspector(s) direct access to all relevant documents and to allocate their time and the time of their staff to discuss any findings/relevant issues.

### **7.9.1 Data Management**

As part of the responsibilities assumed by participating in the study, the principal investigator or subinvestigator agrees to maintain adequate case histories for the patients treated as part of the research under this protocol. The investigator agrees to maintain source documentation as part of the case histories. These source documents may include patient's medical records, hospital charts, clinic charts, the investigator's patient study files, patient diaries, as well as diagnostics tests such as laboratory reports, etc.

Allergan/ [REDACTED] will supply the eCRF.

The principal investigator or designee(s) must enter study data required by the protocol into an electronic data capture (EDC) system. All eCRF fields are to be filled in. If an item is not available or is not applicable, this fact should be indicated. Blank fields should not be present unless otherwise directed. The analysis data sets will be a combination of these data and data from other sources (e.g., laboratory data).

Guidelines for completion of eCRFs will be reviewed with study site personnel at the investigators' meeting/site initiation visits. The principal investigator is responsible for approval of the entered/corrected data. The eCRF responsibilities of the site personnel will be documented on the site delegation log, which will be collected at the closeout visits. Principal investigators or designees must review and approve the data before database lock.

The clinical research associate will visit each study site, at a frequency documented in the monitoring plan, to review eCRFs for completeness and accuracy. Any discrepancies found between source documents and completed eCRFs will be entered as a discrepancy in the EDC system by the clinical research associate. Appropriate study site personnel should then address those discrepancies in the EDC system. Uniform procedures for eCRF correction (queries) will be discussed at the investigators' meeting and during the study site initiation visits.

Data from eCRFs and other external data sources will be entered into a clinical database as specified in the data management plan. Quality control and data validation procedures will be applied to ensure the validity and accuracy of the clinical database.

Computerized and manual procedures should be used to review and check data from eCRFs and data from other external sources for omissions, apparent errors, and values that may require further clarification. Data queries requiring clarification should be documented, and the study site should be requested to review and resolve the queries. Only authorized personnel can make corrections to the clinical database, and all corrections should be documented in an audit trail. A quality assurance audit should be performed before database lock.

After database lock, each study site will receive a CD-ROM containing all of their site-specific eCRF data as entered into EDC for the study, including full discrepancy and

audit history. Additionally, a CD-ROM copy of all of the study site's data from the study will be created and sent to the sponsor for storage.

## **8 Ethics**

### **8.1 Independent Ethics Committee or Institutional Review Board**

The US federal regulations (and applicable local country regulations) and the International Council for Harmonisation (ICH) guidelines require that approval be obtained from an IRB/IEC before participation of human patients in research studies. Before study onset, the protocol, informed consent, advertisements to be used for the recruitment of study patients, and any other written information regarding this study to be provided to the patient or the patient's legal guardian must be approved by the IRB/IEC. Documentation of all IRB/IEC approvals and of the IRB/IEC compliance with ICH harmonised tripartite guideline E6(R1): GCP will be maintained by the site and will be available for review by the sponsor or its designee.

All IRB/IEC approvals should be signed by the IRB/IEC chairman or designee and must identify the IRB/IEC name and address, the clinical protocol by title or protocol number or both, and the date approval or a favorable opinion was granted.

The principal investigator or subinvestigator is responsible for providing written summaries of the progress and status of the study at intervals not exceeding 1 year or otherwise specified by the IRB/IEC. The principal investigator or subinvestigator must promptly supply the sponsor or its designee, the IRB/IEC, and, where applicable, the institution, with written reports on any changes significantly affecting the conduct of the study or increasing the risk to patients.

